## **6.7 IMMUNOGENICITY ANALYSES**

The immunogenicity analysis population will consist of all patients with at least one ADA assessment. Patients will be grouped according to treatment received or, if no treatment is received prior to study discontinuation, according to treatment assigned.

The numbers and proportions of treatment emergent ADA-positive patients and ADA-negative patients at baseline (baseline prevalence) and after drug administration (postbaseline incidence) will be summarized by treatment group. When determining postbaseline incidence, patients are considered to be ADA positive if they are ADA negative or have missing data at baseline but develop an ADA response following study drug exposure (treatment-induced ADA response), or if they are ADA positive at baseline and the titer of one or more postbaseline samples is at least 0.60 titer unit greater than the titer of the baseline sample (treatment-enhanced ADA response). Patients are considered to be ADA negative if they are ADA negative or have missing data at baseline and all postbaseline samples are negative, or if they are ADA positive at

baseline but do not have any postbaseline samples with a titer that is at least 0.60 titer unit greater than the titer of the baseline sample (treatment unaffected).

The relationship between ADA status and safety, activity, PK, and biomarker endpoints may be analyzed and reported via descriptive statistics.

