## **6. STATISTICAL CONSIDERATIONS AND ANALYSIS PLAN**

No formal hypothesis testing is planned. Descriptive statistics will be used to summarize the safety, tolerability, pharmacokinetics, and clinical activity of RO7297089. Data will be described and summarized as warranted by number of patients in question. Listings will be used in place of tables for small numbers of patients. All analyses will be based on the safety-evaluable population, defined as all patients who receive any amount of study drug.

Continuous variables will be summarized using means, standard deviations, median and ranges; categorical variables will be presented using counts and percentages. All summaries will be presented by dose cohort to which a patient was originally assigned.

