### Appendix 3: Schedule of Pharmacokinetic, Immunogenicity, and Biomarker Samples

---

Visit	Timepoint	Sample Type
End of treatment visit	Any time	Flow cytometry and PBMC isolation (whole blood)
		Cell-free DNA (whole blood)
		Peripheral biomarkers (plasma and serum)
		PK (serum)
		ADA (serum)

ADA=anti-drug antibody; C=cycle; D=day; PBMC=peripheral blood mononuclear cell; PK=pharmacokinetic; WGS=whole genome sequencing.

Note: Study assessments may be delayed or moved ahead of the window to accommodate holidays, vacations, and unforeseen delays.

- a Pre-infusion collection should be taken within 2 hours prior to infusion.
- b Whole blood sample for WGS should be collected on Cycle 1, Day 1; however, it may be collected at any time during the study after Cycle 1, Day 1.
- c Cell-free DNA will only be collected on Cycle 4, Day 1.

## Appendix 4

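### Section 6.7 gives one ADA population for both prevalence and incidence, so, read as written, a patient with only a baseline sample stays in the incidence denominator as ADA-negative

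*Combined protocol and SAP*

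**What the plan says.** Section 6.7 defines the population in one sentence: "The immunogenicity analysis population will consist of all patients with at least one ADA assessment". Patients are grouped by treatment received or, "if no treatment is received prior to study discontinuation, according to treatment assigned". Baseline prevalence and the proportions "after drug administration (postbaseline incidence) will be summarized by treatment group" are both reported from this population, and no separate denominator is given for either.

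The ADA-negative group is defined in two parts:
- Baseline negative or missing: "Patients are considered to be ADA negative if they are ADA negative or have missing data at baseline and all postbaseline samples are negative".
- Baseline positive: the patient is negative (treatment unaffected) if positive at "baseline but do not have any postbaseline samples with a titer that is at least 0.60 titer unit greater" than the baseline titer.

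Section 6.7 has no category for patients who cannot be assessed after baseline. The opening of Section 6 carries a general rule: "All analyses will be based on the safety-evaluable population, defined as all patients who receive any amount of study drug".

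Appendix 3 schedules the first ADA sample before the Cycle 1, Day 1 infusion. In Arms A and C the next one is before the Cycle 2, Day 1 infusion; none is listed for Days 2, 3, 8 or 9 of Cycle 1. Arm B has an extra pre-infusion ADA draw on Cycle 1, Day 2. All arms have an ADA sample at the end-of-treatment visit, which Section 4.6.1 and Appendix 1 place 30 (±10) days after the last dose.

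**The concern.** Incidence is meaningful only for patients who could have been observed to develop ADAs. A patient with a baseline sample and nothing afterwards gives no information on that, yet the stated population keeps the patient in the denominator and the stated rules place the patient among the negatives.

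Two outputs are touched. The first is ADA incidence, half of the immunogenicity endpoint in Section 2.4. The second is the set of optional comparisons of safety, PK, activity and biomarkers by ADA status, where untested early dropouts would join the ADA-negative comparator. Early stopping may not be neutral here. Section 5.1.1.1 allows that infusion and hypersensitivity reactions may be accompanied by emergent ADAs, and Table 3 calls for permanent discontinuation after every Grade 4 and some Grade 3 infusion-related reactions.

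**Working it through.** The plan states no ADA rate, no evaluable count and no missing-sample rate, so there is no figure to reproduce. The check applies the written rules to a patient with no post-baseline sample and then compares denominators.

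**Step 1: classification with no post-baseline sample.**
- Baseline positive: the rule asks whether any later sample shows a rise of at least 0.60 titer unit. None exists, so the condition for ADA-negative is met literally.
- Baseline negative or missing: the rule requires that "all postbaseline samples are negative". With no samples this holds only by default, since nothing contradicts it.
- Neither patient can meet a positive definition, because each needs a post-baseline result.

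**Step 2: who this is.** In Arms A and C it is a patient who stops before the Cycle 2, Day 1 draw and also has no end-of-treatment sample, for example through death, withdrawal or a missed visit. In Arm B the Day 2 draw gives most patients a nominal post-baseline sample, but only about a day after first exposure.

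**Step 3: effect on the rate.** Let N be the patients with any ADA sample, k those with no post-baseline sample, and x those classed positive.

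Plan as written: x/N. Assessed patients only: x/(N-k). Ratio of the first to the second: (N-k)/N.

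N=30 is the approximate expansion size (Section 3.1.4). N=3 is the minimum cohort (Section 3.1.1), and N=6 stands for an enlarged cohort. All k and x are assumptions.

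| N | k | x | x/N | x/(N-k) | (N-k)/N |
|---|---|---|---|---|---|
| 30 | 1 | 6 | 20.0% | 6/29 = 20.7% | 0.97 |
| 30 | 3 | 8 | 26.7% | 8/27 = 29.6% | 0.90 |
| 30 | 4 | 6 | 20.0% | 6/26 = 23.1% | 0.87 |
| 30 | 6 | 7 | 23.3% | 7/24 = 29.2% | 0.80 |
| 6 | 2 | 1 | 16.7% | 1/4 = 25.0% | 0.67 |
| 3 | 1 | 1 | 33.3% | 1/2 = 50.0% | 0.67 |

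**Step 4: what the ratio is.** It relates two estimators. It equals the relative bias only if unassessed patients would have had the same ADA rate as assessed ones. With N=30, k=4 and x=6, the rate had all 30 been assessed lies between 6/30 = 20.0% (none of the four positive) and 10/30 = 33.3% (all four positive). The rule as written always reports the lower end.

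**Step 5: untreated patients.** The grouping rule in Section 6.7 provides for patients who received no drug; the opening of Section 6 limits all analyses to patients who did. Both cannot govern. The case should be rare, since for the Cycle 1, Day 1 draw "Pre-infusion collection should be taken within 2 hours prior to infusion": the patient must be bled and then not dosed.

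**The case against.** The strongest reply is that Section 6.7 leaves the incidence denominator unspecified rather than wrong. An ordinary reader takes a statement about all post-baseline samples to presuppose that some exist, and the paragraph ties incidence to the period after drug administration. This is fair for baseline-negative patients, where the result holds only by default. It does not help for baseline-positive patients, who meet the negative rule literally. Nor does it supply another denominator: only one population is stated. Section 6.6, by contrast, says outright how missing response assessments are handled.

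A reader might go further and infer that the plan deliberately counts never-treated patients as ADA-negative. The documents do not support that. The sentence in Section 6.7 is a grouping rule, and the opening of Section 6 would exclude those patients. What stands is a conflict to be reconciled.

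A reader might also infer that every Cycle 1 dropout is affected, or that the factor in the table is a proven bias. Neither follows. The end-of-treatment sample covers patients who attend that visit, and early dropouts with short exposure may have a different ADA rate.

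The effect may also be small beside sampling error. For 6 of 30, Section 6.1 quotes a 90% interval of 8% to 32% (there for response), against a shift of 3.1 points when k=4. In the smallest cohorts, Section 6 replaces tables with listings. Both points limit the consequence; neither makes the denominator right.

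**Conclusion.** The point holds in a limited form. Followed as written, Section 6.7 keeps patients with only a baseline sample in the incidence denominator and the ADA-negative group, so the reported incidence is (N-k)/N times that among assessed patients. The size rests entirely on an assumed k: a factor of 0.97 to 0.80 for N=30 and k=1 to 6, and about 0.67 for one unassessed patient in a cohort of 3 or two in 6. It is probably small in the expansion stage.

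The endpoint is descriptive. Section 6 plans no formal testing, and ADA results enter none of the stopping rules in Section 6.8, so no error rate, sample size or interim decision changes. The correction is still worth making, because it is free and removes untested patients from the ADA-negative comparator.

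**What to change.** In Section 6.7:

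1. Define baseline prevalence in patients with a baseline ADA sample.
2. Define post-baseline incidence, and all comparisons by ADA status, in treated patients with at least one post-baseline ADA sample. Patients with a missing baseline but a later sample can stay in, as the current positive and negative rules already provide.
3. Report by treatment group the number of treated patients with no post-baseline sample, as a separate category and not as ADA-negative.
4. State whether the Arm B Cycle 1, Day 2 pre-infusion draw alone qualifies as a post-baseline sample. If it does, Arm B patients who stop early count as assessed about a day after first exposure, while comparable patients in Arms A and C do not.
5. Reconcile the sentence on untreated patients with the general population rule at the start of Section 6.

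The cost is analysis wording and one extra count per table. No sampling, data collection or sample-size change is needed.

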## **6.8 INTERIM ANALYSES**

Continuous safety monitoring and interim analyses will be performed for the expansion portion of the study to guide potential early stopping of enrollment in the event of unacceptable toxicity or a lower than expected response rate.

A Bayesian posterior probability approach (Thall and Simon 1994) with a uniform prior will be used to evaluate toxicity, including the rate of DLTs. If at any time in the expansion cohort, the number of observed DLTs indicates that there is an approximately 80% chance that the true DLT rate is  $\geq 20\%$  (e.g., DLTs observed in 2/5, 3/10, 4/15, 5/20 patients), accrual to the cohort may be paused and the ISC will meet to determine whether further enrollment in the cohort should be halted taking into account feedback from study investigators.

A similar approach will be used to assess the response rate. Specifically, after approximately 15 patients in the expansion cohort have completed their first tumor assessment, an interim analysis will be conducted to inform potential early stopping of enrollment if observed response rates are lower than expected. Using the Bayesian posterior probability approach with a uniform prior, the cohort may be stopped if the objective response rate is less or equal to 25% with a probability greater or equal to 60%. This would be the case for example if 2 or fewer out of the first 15 patients have an objective response. At each interim analysis, the ISC will review the response data and decide whether to recommend an early decision to stop enrollment in the subgroup due to futility. Additional futility analyses may be conducted in periodic review of efficacy data. In all cases, decisions to stop enrollment into the expansion cohort will be made in consultation with study investigators.

## **7. DATA COLLECTION AND MANAGEMENT**

### **7.1 DATA QUALITY ASSURANCE**

The Sponsor will be responsible for data management of this study, including quality checking of the data. Data entered manually will be collected via EDC through use of eCRFs. Sites will be responsible for data entry into the EDC system. In the event of discrepant data, the Sponsor will request data clarification from the sites, which the sites will resolve electronically in the EDC system.

The Sponsor will produce an EDC Study Specification document that describes the quality checking to be performed on the data. Central laboratory data and all non-CRF data types (i.e., ECG, IxRS, and sample results data) will be sent directly to the Sponsor,

using the Sponsor's standard procedures to handle and process the electronic transfer of these data.

eCRFs and correction documentation will be maintained in the EDC system's audit trail. System backups for data stored by the Sponsor and records retention for the study data will be consistent with the Sponsor's standard procedures.

## **7.2 ELECTRONIC CASE REPORT FORMS**

eCRFs are to be completed through use of a Sponsor-designated EDC system. Sites will receive training and have access to a manual for appropriate eCRF completion. eCRFs will be submitted electronically to the Sponsor and should be handled in accordance with instructions from the Sponsor.

All eCRFs should be completed by designated, trained site staff. eCRFs should be reviewed and electronically signed and dated by the investigator or a designee.

At the end of the study, the investigator will receive patient data for his or her site in a readable format that must be kept with the study records. Acknowledgement of receipt of the data is required.

## **7.3 SOURCE DATA DOCUMENTATION**

Study monitors will perform ongoing source data verification and review to confirm that critical protocol data (i.e., source data) entered into the eCRFs by authorized site personnel are accurate, complete, and verifiable from source documents.

Source documents (paper or electronic) are those in which patient data are recorded and documented for the first time. They include, but are not limited to, hospital records, clinical and office charts, laboratory notes, memoranda, patient-reported outcomes, evaluation checklists, pharmacy dispensing records, recorded data from automated instruments, copies of transcriptions that are certified after verification as being accurate and complete, microfiche, photographic negatives, microfilm or magnetic media, X-rays, patient files, and records kept at pharmacies, laboratories, and medico-technical departments involved in a clinical trial.

Before study initiation, the types of source documents that are to be generated will be clearly defined in the Trial Monitoring Plan. This includes any protocol data to be entered directly into the eCRFs (i.e., no prior written or electronic record of the data) and considered source data.

Source documents that are required to verify the validity and completeness of data entered into the eCRFs must not be obliterated or destroyed and must be retained per the policy for retention of records described in Section 7.5.

To facilitate source data verification and review, the investigators and institutions must provide the Sponsor direct access to applicable source documents and reports for trial-related monitoring, Sponsor audits, and IRB/EC review. The study site must also allow inspection by applicable health authorities.

#### **7.4 USE OF COMPUTERIZED SYSTEMS**

When clinical observations are entered directly into a study site's computerized medical record system (i.e., in lieu of original hardcopy records), the electronic record can serve as the source document if the system has been validated in accordance with health authority requirements pertaining to computerized systems used in clinical research. An acceptable computerized data collection system allows preservation of the original entry of data. If original data are modified, the system should maintain a viewable audit trail that shows the original data as well as the reason for the change, name of the person making the change, and date of the change.

#### **7.5 RETENTION OF RECORDS**

Records and documents pertaining to the conduct of this study and the distribution of IMP, including eCRFs, Informed Consent Forms, laboratory test results, and medication inventory records, must be retained by the Principal Investigator for 15 years after completion or discontinuation of the study or for the length of time required by relevant national or local health authorities, whichever is longer. After that period of time, the documents may be destroyed, subject to local regulations.

No records may be disposed of without the written approval of the Sponsor. Written notification should be provided to the Sponsor prior to transferring any records to another party or moving them to another location.

Roche will retain study data for 25 years after the final study results have been reported or for the length of time required by relevant national or local health authorities, whichever is longer.

### **8. ETHICAL CONSIDERATIONS**

#### **8.1 COMPLIANCE WITH LAWS AND REGULATIONS**

This study will be conducted in full conformance with the ICH E6 guideline for Good Clinical Practice and the principles of the Declaration of Helsinki, or the applicable laws and regulations of the country in which the research is conducted, whichever affords the greater protection to the individual. The study will comply with the requirements of the ICH E2A guideline (Clinical Safety Data Management: Definitions and Standards for Expedited Reporting). Studies conducted in the United States or under a U.S. Investigational New Drug (IND) Application will comply with U.S. FDA regulations and applicable local, state, and federal laws. Studies conducted in the European Union or European Economic Area will comply with the E.U. Clinical Trial Directive (2001/20/EC) and applicable local, regional, and national laws.

## **8.2 INFORMED CONSENT**

The Sponsor's sample Informed Consent Form (and ancillary sample Informed Consent Forms such as an Assent Form or Mobile Nursing Informed Consent Form, if applicable) will be provided to each site. If applicable, it will be provided in a certified translation of the local language. The Sponsor or its designee must review and approve any proposed deviations from the Sponsor's sample Informed Consent Forms or any alternate consent forms proposed by the site (collectively, the "Consent Forms") before IRB/EC submission. The final IRB/EC-approved Consent Forms must be provided to the Sponsor for health authority submission purposes according to local requirements.

If applicable, the Informed Consent Form will contain separate sections for any optional procedures. The investigator or authorized designee will explain to each patient the objectives, methods, and potential risks associated with each optional procedure. Patients will be told that they are free to refuse to participate and may withdraw their consent at any time for any reason. A separate, specific signature will be required to document a patient's agreement to participate in optional procedures. Patients who decline to participate will not provide a separate signature.

The Consent Forms must be signed and dated by the patient or the patient's legally authorized representative before his or her participation in the study. The case history or clinical records for each patient shall document the informed consent process and that written informed consent was obtained prior to participation in the study.

The Consent Forms should be revised whenever there are changes to study procedures or when new information becomes available that may affect the willingness of the patient to participate. The final revised IRB/EC-approved Consent Forms must be provided to the Sponsor for health authority submission purposes.

If the Consent Forms are revised (through an amendment or an addendum) while a patient is participating in the study, the patient or a legally authorized representative must re-consent by signing the most current version of the Consent Forms or the addendum, in accordance with applicable laws and IRB/EC policy. For any updated or revised Consent Forms, the case history or clinical records for each patient shall document the informed consent process and that written informed consent was obtained using the updated/revised Consent Forms for continued participation in the study.

A copy of each signed Consent Form must be provided to the patient or the patient's legally authorized representative. All signed and dated Consent Forms must remain in each patient's study file or in the site file and must be available for verification by study monitors at any time.

For sites in the United States, each Consent Form may also include patient authorization to allow use and disclosure of personal health information in compliance with the U.S. Health Insurance Portability and Accountability Act (HIPAA) of 1996. If the site utilizes a

separate Authorization Form for patient authorization for use and disclosure of personal health information under the HIPAA regulations, the review, approval, and other processes outlined above apply except that IRB review and approval may not be required per study site policies.

### **8.3 INSTITUTIONAL REVIEW BOARD OR ETHICS COMMITTEE**

This protocol, the Informed Consent Forms, any information to be given to the patient, and relevant supporting information must be submitted to the IRB/EC by the Principal Investigator and reviewed and approved by the IRB/EC before the study is initiated. In addition, any patient recruitment materials must be approved by the IRB/EC.

The Principal Investigator is responsible for providing written summaries of the status of the study to the IRB/EC annually or more frequently in accordance with the requirements, policies, and procedures established by the IRB/EC. Investigators are also responsible for promptly informing the IRB/EC of any protocol amendments (see Section 9.6).

In addition to the requirements for reporting all adverse events to the Sponsor, investigators must comply with requirements for reporting serious adverse events to the local health authority and IRB/EC. Investigators may receive written IND safety reports or other safety-related communications from the Sponsor. Investigators are responsible for ensuring that such reports are reviewed and processed in accordance with health authority requirements and the policies and procedures established by their IRB/EC, and archived in the site's study file.

